9.1.4 Non-target Lesions

All other lesions (or sites of disease) including any measurable lesions over and above the 5 target lesions should be identified as non-target lesions and should also be recorded at baseline. Measurements of these lesions are not required, but the presence, absence, or in rare cases unequivocal progression of each should be noted throughout follow-up.

9.1.5 Evaluation of Target Lesions

NOTE: In addition to the information below, also see the international criteria proposed by the Response Evaluation Criteria in Solid Tumors (RECIST) Committee, version 1.1 (Eur J Cancer 45;2009:228-247) for special notes on the assessment of target lesions.

Complete Response (CR)	Disappearance of all target lesions. Any pathological lymph nodes (whether target or non-target) must have reduction in short axis to <10 mm.
Partial Response (PR)	At least a 30% decrease in the sum of the diameters of target lesions, taking as reference the baseline sum diameters
Progressive Disease (PD)	At least a 20% increase in the sum of the diameters of target lesions, taking as reference the smallest sum on study (this includes the baseline sum if that is the smallest on study). In addition to the relative increase of 20%, the sum must also demonstrate an absolute increase of at least 5 mm. (Note: the appearance of one or more new lesions is also considered progressions).
Stable Disease (SD)	Neither sufficient shrinkage to qualify for PR nor sufficient increase to qualify for PD, taking as reference the smallest sum diameters while on study

9.1.6 Evaluation of Non-Target Lesions

Complete Response (CR)	Disappearance of all non-target lesions and normalization of tumor marker level. All lymph nodes must be non-pathological in size (<10 mm short axis). NOTE: If tumor markers are initially above the upper normal limit, they must normalize for a subject to be considered in complete clinical response.
Non-CR/ Non-PD	Persistence of one or more non-target lesion(s) and/or maintenance of tumor marker level above the normal limits
Progressive Disease (PD)	Appearance of one or more new lesions and/or unequivocal progression of existing non-target lesions. Unequivocal progression should not normally trump target lesion status. It must be representative of overall disease status change, not a single lesion increase.

Although a clear progression of “non-target” lesions only is exceptional, the opinion of the site investigator should prevail in such circumstances, and the progression status should be confirmed at a later time by the sponsor investigator.

9.1.7 Evaluation of Best Overall Response

Target Lesions	Non-Target Lesions	New Lesions	Overall Response
CR	CR	No	CR
CR	Non-CR/ Non-PD	No	PR
CR	Not evaluated	No	PR
PR	Non-PD/ or not all evaluated	No	PR
SD	Non-PD or not all evaluated	No	SD
Not all evaluated	Non-PD	No	Non-evaluable
PD	Any	Yes or No	PD
Any	PD*	Yes or No	PD
Any	Any	Yes	PD

*In exceptional circumstances, unequivocal progression in non-target lesions may be accepted as disease progression.

Subjects with a global deterioration of health status requiring discontinuation of treatment without objective evidence of disease progression at that time should be classified as having “symptomatic deterioration.” Every effort should be made to document the objective progression even after discontinuation of treatment.

In some circumstances, it may be difficult to distinguish residual disease from normal tissue. When the evaluation of complete response depends on this determination, it is recommended that the residual lesion be investigated (fine needle aspirate/biopsy) to confirm the complete response status.

9.2 Definitions for Response Evaluation – RANO -BM

MRI scan of head at screening and every other treatment cycle (i.e. 6 weeks) through week 48, then every 9 weeks (i.e. every 3 cycles) until documented disease progression starting after treatment initiation with Cycle 1. Given that imaging following immunotherapy differs greatly from what is typically seen following chemoradiation treatment or treatment with anti-angiogenic compounds, evaluation of response using Macdonald criteria or Response Assessment in Neuro-Oncology (RANO) criteria is not appropriate in this trial. Due to differences in the nature of primary brain tumors and brain metastases, a modified version of RANO called RANO-BM will be used.

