2.2 Endpoints

2.2.1 Primary Endpoint

- Intracranial PFS is defined as the time from Day 1 of treatment until the criteria for intracranial disease progression is met as defined by RANO-BM or death as a result of any cause, whichever comes first.

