5. TREATMENT PLAN

This is a single arm, multicenter phase II trial for 60 patients with untreated extensive stage (ES) small cell lung cancer (SCLC) with asymptomatic brain metastases. Subjects will receive 4 cycles of induction treatment with Atezolizumab (1200 mg on Day 1) combined with carboplatin (5-6 AUC on Day 1) and etoposide (80-100 mg/m² on Days 1-3). Each cycle equals 21 days. After 4 cycles of induction treatment, subjects will receive atezolizumab maintenance 1200 mg on Day 1 of each 3-week cycle. Subjects will receive treatment until disease progression, unacceptable drug-related toxicity, or withdrawal from study for any reason.

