- 4: CBC with platelet and differential (white blood cell count, absolute neutrophil count, hemoglobin and platelet count). Serum chemistries (creatinine, glucose, total bilirubin, aspartate transaminase [AST] and alanine transaminase [ALT] and calcium). Thyroid Function testing should be performed at screening then every 6 weeks (i.e. every other cycle). TSH will be obtained. T4 and T3 including free versus total testing is at the discretion of the site investigator. Hepatitis testing to be performed at screening if results as described in the inclusion criteria are not known. For women of childbearing potential (WOCBP): urine or serum β hCG if clinically appropriate. If a urine test is done and it is positive or cannot be confirmed as negative, a serum pregnancy test will be required. Testing is required within 24 hours prior to initiation of study treatment. During treatment, testing should be performed every 3 weeks (on Day 1 of each cycle prior to administering treatment).
- 5: Tumor response assessment will consist of evaluation by MRI scan of the brain and CT scans of chest +/- abdomen and pelvis. If unable to perform MRI due to medical reasons, CT with contrast is acceptable. Brain MRI used to diagnose brain metastases allowed or a CT with contrast is acceptable. The abdomen/pelvis may be scanned at follow-up timepoints only if positive disease was detected at baseline. Radiology imaging to be performed at screening (within 6 weeks prior to C1D1), then every 6 weeks (prior to Cycle 3 Day 1 and Cycle 6 Day 1) then every 9 weeks (prior to Cycle 9 and so on). Imaging needs to occur every time point regardless of any delay in treatment. Tumor imaging to be done in the follow up period is at discretion of site investigator. If tumor assessments are available for subjects who have not yet experienced progressive disease (PD) at the time treatment is discontinued, the follow-up tumor evaluations will be documented in the eCRF until PD or death is confirmed, or until another treatment is initiated.
- 6: Induction treatment will consist of 4 cycles of Atezolizumab (1200 mg on Day 1) combined with carboplatin (5-6 AUC on Day 1) and etoposide (80-100 mg/m² on Days 1-3). After 4 cycles of induction treatment, subjects will receive atezolizumab maintenance 1200 mg on Day 1 of each 3-week cycle. Subjects will receive treatment until disease progression, unacceptable drug-related toxicity, or withdrawal from study for any reason.

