- 7: Archival tissue is required if available. Archival tissue should be identified and requested at screening and shipped by Cycle 2 Day 1, if available. If archival tissue is not available, the subject may still be eligible for the trial. See CLM for collection, labeling, and shipping instructions. Subjects will also be consented for optional storage of any remaining tissue samples after protocol-specified studies are complete. These samples will be stored for future unspecified cancer-related research and are considered “banking samples”.

8: Blood (whole blood for PBMCs, plasma and buffy coat for germline DNA) for correlative analysis will be drawn prior to treatment on Cycle 1 Day1, Cycle 3 Day 1 and at the D30 safety visit/progression. Additional details regarding correlatives can be found in Section 8 and the CLM.

9: If screening (baseline) CBC and Chemistry (CMP) were performed within 7 days of Day 1 of treatment, these do not need to be repeated. All laboratory assessments should be done prior to treatment.

10: Safety Follow Up: The safety follow-up visit should only occur when subjects permanently stop study treatment for whatever reasons (toxicity, progression, or other reason) and should be performed 30 days (+ 7 days) after the last dose of treatment. Subjects who have an ongoing Grade ≥ 2 or serious AE (SAE) at this visit will continue to be monitored by a member of the study team until the event is resolved, stabilized, determined to be irreversible by the site investigator or a new anti-cancer treatment starts, whichever occurs earlier.

11: Long Term Follow Up: For subjects who discontinue for reasons other than progressive disease, radiographic disease assessment should be performed every 9 weeks until progression, initiating a new cancer treatment, withdrawing consent or becoming lost to follow-up. The scan interval may be reset if scans were done sooner for clinical reasons and the type of scan may be left to discretion of the site investigator. This imaging may be done locally. Once disease progression is documented, subjects will be followed for survival every 3 months for 1 year from documented progression. Follow up may be accomplished via clinic visit, phone call, or other avenues as appropriate. A window of ± 14 days will be applied to follow up.

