9.2.5 Evaluation of best overall CNS response

Target Lesions	Non-Target Lesions	New Lesions**	Corticosteroids	Clinical status	Overall Response
None	None	None	None	Stable or improved	CR
≥30% decrease in sum longest distance relative to baseline	Stable or improved	None	Stable or decreased	Stable or improved	PR
<30% decrease relative to baseline but <20% increase in sum longest distance relative to nadir	Stable or improved	None	Stable or decreased	Stable or improved	SD

$\geq 20\%$ increase in sum longest distance relative to nadir*	Uequivocal progressive disease*	Present*	N/A	Worse*	PD

*Progression occurs when any of these criteria are met. If ≤ 6 months from initiation of immunotherapy, radiographic progression (including new lesions) with no new or significantly worsened neurologic deficits not due to co-morbid event or concurrent medication should be confirmed on follow-up imaging 3 months after initial radiographic progression (if progression confirmed, the date of actual progression should be back-dated to the date of initial radiographic progression). **A new lesion is one that is not present on prior scans and is visible in minimum two projections. If a new lesion is equivocal, for example because of its small size, continued therapy can be considered, and follow-up assessment will clarify if the new lesion is new disease. If repeat scans confirm there is definitely a new lesion, progression should be declared using the date of the initial scan showing the new lesion.
					

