12.3 Sample Size and Accrual

The study will enroll 63 eligible patients who receive at least one dose of the study agent.

The sample size of the study is determined by the analysis of iPFS. To detect an improvement of median iPFS = 5.2 months from 4.0 months in historical control (IMpower 133) (HR = 0.77) using a logrank test, 60 treated patients will be required to achieve approximately 81% power at a one-sided significance level of 0.15. Patients are accrued for a period of 22 months. Follow-up continues for 12 months after the last patient is enrolled. The probability that a patient experiences an event during the study is 0.9707. The expected number of events during the study is 58. It is assumed that the survival time is exponentially distributed. The sample size calculation above is conducted in PASS v16.0.2. Assuming a 5% rate of dropout prior to protocol treatment, a total of 63 eligible patients will be treated by at least one doses of the study agent.

The sample size calculation is determined to have adequate power to reject the null hypothesis when the alternative hypothesis is true for the primary endpoint iPFS. Whether it has sufficient power for addressing secondary endpoints or exploratory analysis is not of concern.

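### Section 9.2 and calendar footnote 5 give different brain-MRI schedules for the scan that dates the primary endpoint; following one rather than the other moves median iPFS by about 1 week on average

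*Combined protocol and SAP*

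**What the plan says.** - **Section 9.2 (RANO-BM):** head MRI "every other treatment cycle (i.e. 6 weeks) through week 48, then every 9 weeks (i.e. every 3 cycles) until documented disease progression".
- **Section 7, calendar footnote 5**, which names brain MRI as part of tumour assessment: imaging "every 6 weeks (prior to Cycle 3 Day 1 and Cycle 6 Day 1) then every 9 weeks (prior to Cycle 9" and so on. It adds: "Imaging needs to occur every time point regardless of any delay in treatment".
- **Section 5:** "Each cycle equals 21 days".
- **Section 1.4** summarises restaging as 6-weekly and mentions no later change of interval.
- **Section 2.2.1:** iPFS runs from Day 1 "until the criteria for intracranial disease progression is met as defined by RANO-BM", or death.
- **Section 9.2.5:** when an early radiographic progression is confirmed later, "the date of actual progression should be back-dated to the date of initial radiographic progression". A confirmed new lesion likewise takes the date of the scan that first showed it.
- **Sections 12.3 and 12.6.1:** the trial is sized for an "improvement of median iPFS = 5.2 months from 4.0 months in historical control" by a log-rank test. The primary analysis reports the Kaplan-Meier median and 6-month iPFS.

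**The concern.** Sections 7 and 9.2 are both current, operative instructions for the same scan, and they disagree. Footnote 5 also disagrees with itself: Cycle 3 to Cycle 6 is three cycles, or 9 weeks, not 6. The change of interval at week 48 appears only in section 9.2. Footnote 5 also names its time points by cycle while requiring imaging whether or not treatment is delayed, so after a delay it is unclear which date is meant. The visit windows (2 days in the calendar, 3 and 7 days in section 5.1) cannot absorb gaps of 3 to 6 weeks.

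A progression found by imaging is recorded at the next scheduled scan, so the schedule is part of how iPFS is measured. In a multicentre trial, sites could date the same course differently. The result is then compared with a fixed historical median, with no concurrent arm in which the same difference would cancel.

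**Working it through.** **1. The plan's own figure.** A one-sample log-rank test against an exponential with median 4.0 months, with true median 5.2 months, N = 60 and one-sided alpha 0.15, gives power of 0.80 to 0.82 by asymptotic formulae and 0.813 by simulation. The plan states about 81%. This supports treating the planned test as a single-arm comparison, which is assumed in step 6.

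**2. Scan weeks.** Cycle k Day 1 falls at week 3(k − 1), so C3 = 6, C6 = 15, C9 = 24 and C12 = 33.

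| Reading | Scan weeks |
|---|---|
| Section 9.2 | 6, 12, 18, 24, 30, 36, 42, 48, 57, 66 … |
| Footnote 5, cycle labels | 6, 15, 24, 33 … |
| Footnote 5, stated intervals | 6, 12, 21, 30 … |

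In weeks, 4.0, 5.2 and 6 months are 17.4, 22.6 and 26.1. The target gain of 1.2 months is 22.6 − 17.4 = 5.2 weeks.

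**3. Individual dates, labels minus section 9.2.** By week of true progression: 0–6: 0; 6–12: +3; 12–15: −3; 15–18: +6; 18–24: 0; 24–30: +3; 30–33: −3; 33–36: +6; 36–42: 0; 42–48: +3; then −6 and +3 in turn as both grids run 9-weekly. Weight these by an exponential with median 4.0 months, S(t) = 0.5^(t/17.4), with every event scan-dated:

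| Difference | Share |
|---|---|
| 0 | 36.7% |
| +3 weeks | 38.2% |
| −3 weeks | 10.4% |
| +6 weeks | 9.2% |
| −6 weeks | 5.5% |

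So 47% are later, 16% are earlier, and the mean is about +1.1 weeks. Progressions by week 48 whose date differs make up 49% of all progressions. For the stated intervals against section 9.2, 35% differ and the mean is +0.8 week.

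**4. Where the median is read.** With no deaths, the population curve steps down only at scan weeks.
- True median 4.0 months: S(15) = 0.550, S(18) = 0.488, S(24) = 0.384. The curve first drops below 0.5 at week 18 on section 9.2, but not until week 24 on the labels.
- True median 5.2 months: S(18) = 0.576, S(24) = 0.479. Both grids read week 24.
- 6-month iPFS (week 26.1): the last scan is week 24 on section 9.2 and on the labels, so the rate is the same. On the stated intervals it is week 21, where S = 0.433. Simulation at 4.0 months gave 0.385, 0.385 and 0.433 respectively.

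**5. Simulated trials.** N = 60, 22 months' accrual, 12 months' follow-up. Progressions move to the next scan, deaths are dated exactly, and progression-free patients are censored at the last scan. The share of first events that are deaths is not in the documents, so it was varied. Mean shift in the Kaplan-Meier median, labels minus section 9.2, in weeks:

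| True median | 0% deaths | 25% | 50% |
|---|---|---|---|
| 3.3 months | +1.00 | +0.62 | +0.61 |
| 3.5 months | +1.44 | +0.73 | +0.52 |
| 4.0 months | +1.71 | +1.22 | +0.70 |
| 5.2 months | +1.47 | +1.15 | +0.88 |

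Monte Carlo standard errors are 0.02 to 0.07. Visit windows of 3 or 7 days hardly matter (+1.15 and +1.21 at 4.0 months, 25% deaths). With 25% deaths plus 25% other events dated off the grid, the shift is +0.48 to +0.93. A separate simulation with death shares of 0, 20 and 40% and true medians of 4 to 6 months gave about +0.8 to +1.8.

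**6. Test decision.** Z = (E − O)/√E, with E from the 4.0-month exponential and cut-off 1.036 (one-sided 0.15). Share of trials in which the same patients give different decisions on section 9.2 and on the labels, at 0/25/50% deaths:
- 3.3 months: 4.2/2.2/0.8%
- 4.0 months: 12.9/9.9/5.7%
- 5.2 months: 1.9/2.4/2.0%

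**The case against.** The textual conflict is not in dispute. The case against concerns how much it matters.

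- **The shift is an average.** In one trial's paired medians it is negative in roughly 22–30% of trials at 4.0 months and in about 40% at 3.3–3.5 months. At 5.2 months it is exactly zero in about 54%. This stands: the fair description is often nothing, sometimes several weeks either way, about +1 week on average.
- **It is small at the design alternative.** At 5.2 months the typical median is week 24 on both section 9.2 and the labels, 6-month iPFS agrees between those two, and decisions differ in about 2% of trials. This also stands. The larger disagreement arises near 4.0 months and rests on an assumed one-sample log-rank test.
- **It compares extremes.** The main figures set all sites on one reading against all sites on the other. If half the patients follow each section, the average shift is about +0.3 to +1.2 weeks.
- **Not every event depends on the grid.** Deaths and progressions called on clinical worsening do not. After treatment stops without progression, imaging is 9-weekly and "the type of scan may be left to discretion of the site investigator". Treating these events as exactly dated is a simplification, but a rough model of patients leaving treatment still gave +0.9 to +1.6 weeks.
- **Section 1.4 is only a summary.** Agreed: the conflict lies between sections 7 and 9.2.

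These points limit the size of the effect. None of them says which schedule applies.

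**Conclusion.** The concern holds. The documents give incompatible schedules for the scan that dates the primary endpoint, and no precedence rule. That follows from the text alone. On average the cycle labels put the Kaplan-Meier median about 0.5 to 1.8 weeks later than section 9.2, or 10% to 35% of the 5.2-week target gain (0.5/5.2 and 1.8/5.2). The effect on a single trial is variable and often nil.

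The size rests on exponential event times, an assumed share of deaths, and scans done on schedule. No effect on type I error is claimed, because the documents do not say whether the 4.0-month control carries its own scan delay; the figures describe only disagreement between readings of this plan. The effect is modest, but it is avoidable, and scan dates cannot be harmonised once collected.

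**What to change.** Reconcile footnote 5 with section 9.2 to a single brain-MRI schedule, and align the summary in section 1.4. State it in weeks from Day 1 rather than by cycle, make it explicitly independent of treatment delay, and apply it at all sites. If the interval changes, give the week of the change once. The choice of interval is the sponsor's.

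The scan-dated Kaplan-Meier and log-rank analysis can stay as planned. It would help, though it is optional, to report the actual MRI intervals by site, so a reader can see whether both schedules were in use before the clarification.

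The cost is a protocol clarification and a notice to sites; any site already scanning on the other grid would have to switch. The optional report needs MRI dates in the database, which is assumed.

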9.2.1 Measurable disease

Measurable disease is defined as a contrast-enhancing lesion that can be accurately measured in at least one dimension, with a minimum size of 10 mm, and is visible on two or more axial slices that are preferably 5 mm or less apart with 0 mm skip (and ideally ≤ 1.5 mm apart with 0 mm skip). Additionally, although the longest diameter in the plane of measurement is to be recorded, the diameter perpendicular to the longest diameter in the plane of measurement should be at least 5 mm for the lesion to be considered measurable. Cystic lesions or surgical cavities should generally be considered non-measurable unless there is a nodular component that measures 10mm or more in longest diameter and 5mm or more in the perpendicular plane. The cystic or surgical cavity should not be measured for the determination of a response.

Non-measurable lesions

Non-measurable disease includes all other lesions, including lesions with longest dimension less than 10 mm, lesions with borders that cannot be reproducibly measured, dural metastases, bony skull metastases, cystic-only lesions, and leptomeningeal disease.

9.2.2 Tumor response assessment

Assignment of CNS response is independent of systemic disease response. All baseline assessments should be done as close as possible to the treatment start and no more than 4 weeks before the beginning of treatment. When more than one measurable lesion in the CNS is present at baseline, all lesions up to a maximum of five CNS lesions should be identified as target lesions and will be recorded and measured at baseline. Target lesions should be selected on the basis of their size (longest diameter) and as those that can be measured reproducibly. A sum of the diameters for all target lesions will be calculated and reported as the baseline sum of longest diameters. All other CNS lesions should be identified as non-target lesions and should also be recorded at baseline.

9.2.3 Evaluation of target lesions

Complete Response (CR)	Disappearance of all CNS target lesions sustained for at least 4 weeks; with no new lesions, no use of corticosteroids, and patient is stable or improved clinically.
Partial Response (PR)	At least a 30% decrease in the sum longest diameter of CNS target lesions, taking as reference the baseline sum longest diameter sustained for at least 4 weeks; no new lesions; stable to decreased corticosteroid dose; stable or improved clinically.

Progressive Disease (PD)	At least a 20% increase in the sum longest diameter of CNS target lesions, taking as reference the smallest sum on study (this includes the baseline sum if that is the smallest on study). In addition to the relative increase of 20%, at least one lesion must increase by an absolute value of 5 mm or more to be considered progression.
Stable Disease (SD)	Neither sufficient shrinkage to qualify for partial response nor sufficient increase to qualify for progressive disease, taking as reference the smallest sum longest diameter while on study.

